5.4. Multicenter Studies

This is a multicenter study. Enrollment by center will be summarized. Due to limited sample size, analyses will not be conducted by center.

5.5. Multiple Comparisons/Multiplicity

The error spending for interim analysis is described in Section 5.16. No other multiple comparison/multiplicity adjustments will be made.

5.6. Patient Disposition

A detailed description of patient disposition will be provided. It will include a summary of the number and percentage of patients entered into the study, enrolled in the study, reasons for discontinuation from study treatment, and reasons for discontinuation from the study. Reason for discontinuation from both study treatment and the study will be listed by the pre-determined categories. If the reason for discontinuation is adverse event (AE) or death, the associated AE or cause of death will be reported. All patients entered in the study will be included in the summary.

5.7. Patient Characteristics

Patient characteristics will be listed for all patients on therapy by cohort, including:

- Patient demographics (including age, sex, race, screening height and weight, and screening derived body surface area)
- Baseline disease characteristics (including basis for initial diagnosis, initial pathological diagnosis, stage at initial diagnosis, baseline Eastern Cooperative Oncology Group performance status)

5.8. Treatment Compliance

The study treatment will be administered only at the investigational sites by the authorized study site personnel. As a result, treatment compliance is ensured. Patients should attend scheduled clinic visits and must comply with study criteria under their control. Deviations from the prescribed dosage regimen should be recorded on the case report form and listed.

5.9. Concomitant Therapy

All medications will be coded to the generic preferred name according to the current World Health Organization drug dictionary. All concomitant medications will be listed and summarized using the preferred name for all patients on therapy by cohort. If concomitant medication use is due to an AE, the associated National Cancer Institute's Common Terminology Criteria for Adverse Events (CTCAE) v4.0 (NCI 2009) term will be listed.

5.10. Efficacy Analyses

5.10.1. Primary Outcome and Methodology

Best overall response (BOR) is defined as the best response recorded from the start of the study treatment until the end of treatment taking into account any requirement for confirmation, and will be derived based on investigator assessment of response and Response Evaluation Criteria in Solid Tumors (RECIST 1.1) (Eisenhauer et al. 2009).

Overall response rate is defined as the number of patients who achieve a BOR of CR or PR, divided by the total number of patients enrolled to the corresponding cohort (full analysis set). Complete or partial responses may be claimed only if the criteria for each are met at a subsequent time point (greater than 4 weeks). The ORR, with exact 95% and 80% CIs, will be summarized for each cohort using the Clopper-Pearson method.

5.10.2. Secondary Efficacy Analyses

Secondary efficacy variables are defined as follows:

Disease control rate is defined as the number of patients who achieve a BOR of CR, PR, or stable disease (SD) divided by the total number of patients enrolled to the corresponding cohort (full analysis set). The confirmation of CR and PR is required. The BOR for patients with an unconfirmed PR or CR observation will be classified as SD, as long as they otherwise meet those requirements (see following sentence). In the case of SD, measurements must have met the SD criteria at least once after study entry at a minimum interval (not less than 5 weeks). The DCR, with exact 95% CI, will be summarized for each cohort using the Clopper-Pearson method.

Duration of response is defined as the time from the date measurement criteria for CR or PR (whichever is first recorded) are first met until the first date that disease is recurrent or objective progression is observed, per RECIST 1.1 criteria, or the date of death from any cause in the absence of objectively determined disease progression or recurrence.

Overall survival is defined as the time from enrollment until death from any cause. If the patient is alive or lost to follow-up at the time of data analysis, OS data will be censored on the last date the patient is known to be alive. Overall survival curves, median OS, and OS rates at various time points with 95% CI, for each cohort will be estimated using the Kaplan-Meier method (Kaplan and Meier 1958).

Progression-free survival is defined as the time from enrollment until the first radiographic documentation of progression or death from any cause in the absence of PD. Patients known to be alive and without disease progression will be censored at the time of the last adequate tumor assessment prior to study completion (a detailed PFS event/censoring scheme is provided in [Table JTJH.5.2](#)). Progression-free survival curves, median PFS, and PFS rates at various time points with 95% CI for each cohort will be estimated using the Kaplan-Meier method (Kaplan and Meier 1958).

Table JTJH.5.2. PFS Event/Censoring Scheme

Situation ^a	Event/Censor	Date of Event or Censor
Tumor progression or death	Event	Earliest date of PD or death
No tumor progression and no death	Censored	Date of last adequate radiological assessment or date of enrollment (whichever is later) ^b
Unless		
No baseline radiological tumor assessment available	Censored	Date of enrollment
No adequate postbaseline radiological tumor assessment available and death reported after 2 scan intervals following enrollment ^{b,c}	Censored	Date of enrollment
Tumor progression or death documented immediately after 2 or more scan intervals following last adequate radiological tumor assessment or enrollment (whichever is later) ^{b,c}	Censored	Date of last adequate radiological assessment or date of enrollment (whichever is later) ^b

Abbreviations: CR = complete response; PD = progressive disease; PFS = progression-free survival; PR = partial response; SD = stable disease.

- a Symptomatic deterioration (that is, symptomatic progression that is not radiologically confirmed) will not be considered as tumor progression.
- b Adequate radiological tumor assessment refers to an assessment with one of the following responses: CR, PR, SD, or PD.
- c For the first 52 weeks following enrollment, radiologic imaging for tumor assessment will be performed approximately every 6 weeks (that is, every 3 cycles) starting at the end of Cycle 3. Thereafter, it will be performed approximately every 12 weeks. The same method of imaging used at baseline should be used for each subsequent assessment. Scans should also be obtained as clinically indicated.

5.11. Health Outcomes/Quality-of-Life Analyses

For the LCSS, the compliance rate by cohort will be calculated as the number of completed assessments divided by the number of expected assessments (that is, patients still on study). Compliance rates, reasons for noncompliance, and data collected will be summarized for all patients (cohort 1 and 2) and by cohort.

The ASBI will be calculated as the mean of 6 symptom-specific questions; the total LCSS score will be calculated as the mean of 9 questions from the LCSS. For a given assessment, if any of the 6 symptom-specific questions have not been completed, the ASBI will not be calculated. Similarly, if any of the 9 LCSS questions have not been completed, the total LCSS score will not be calculated.

Change in tumor size (defined as the percent change in tumor size from the baseline evaluation to the evaluation at the time point where BOR is observed. The correlation between CTS and LCSS score and ASBI will be tested using the Spearman's correlation coefficient.

Descriptive statistics for each of the domain scores/items of interest by category of BOR (that is, CR, PR, SD, PD) will be summarized and a linear model will be fitted for each cohort in order to evaluate the association between BOR and change from baseline/the maximum improvement

from baseline in lung cancer-specific symptoms, symptomatic distress, activity status, overall quality of life, total LCSS score, and ASBI for patients who have platinum-sensitive or platinum-resistant/refractory SCLC. The model will include change from baseline/maximum change from baseline as the response variable and category of best overall response as an independent variable.

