	Plasma biomarker sample	X				X		Collect prior to dosing on Day 1 of Cycles 1 and 3 only.
	ECG	X		X		X		Single local ECG collected at each time point. Day 1: predose, 10 min after EOI (±5 min), 30 min after EOI (±10 min), and >1 hour after EOI. Cycle 2-X: predose. However, if QTcF >480 msec is observed on Day 1, then 10 min after EOI (±5 min), 30 min after EOI (±10 min), and >1 hour after EOI should also be collected in subsequent cycles.
Optional Tumor Biopsy			X				Can occur at any time during patient's treatment.	

Study Period		Study Treatment Period						
		1		2		3-n ^a		
Cycle/Visit		14 days		14 days		14 days		
Duration		14 days		14 days		14 days		
Relative Day within Dosing Cycle		1	8	1	8	1	8	
Tumor Assessment	Radiologic imaging according to RECIST 1.1						X	For the first 52 weeks following enrollment, perform approximately every 6 weeks starting at the end of Cycle 3 (eg, Days 8-14). Thereafter, perform approximately every 12 weeks. The scanning interval (6 or 12 weeks [± 1 week]) should be maintained even if cycles are delayed. As a result, after Cycle 3, the scans may not always occur at the end of a cycle. The same method of imaging used at baseline should be used for each subsequent assessment. Scans should also be obtained as clinically indicated.
Tumor Assessment	Tumor measurement (palpable or visible)						X	Perform at least every 6 weeks starting in Cycle 3 on the same day as the radiologic imaging.
Adverse Events Collection/ CTCAE Grading		X		X		X		
Concomitant Medication Notation		X		X		X		
Lung Cancer Symptom Scale		X		X		X		The LCSS is to be administered prior to extensive interaction with site personnel and prior to administration of study drug.
Study Treatment	LY2606368	X		X		X		IV over approximately 60 (+10) min

Abbreviations: BSA = body surface area; CT = computed tomography; CTCAE = Common Terminology Criteria for Adverse Events (NCI 2009); ECG = electrocardiogram; ECOG = Eastern Cooperative Oncology Group (Oken et al. 1982); EOI = end of infusion; IV = intravenous; min = minute; LCSS = Lung Cancer Symptom Scale; PK = pharmacokinetic; QTcF = QT interval using Fridericia’s correction; RECIST 1.1 = Response Criteria In Solid Tumors Version 1.1 (Eisenhauer et al. 2009).

Table JTJH.2.3. Post-Treatment Follow-Up Schedule of Activities

Study Period		Post-discontinuation Follow-Up		
		Short-term Follow-Up	Long-term Follow-Up	
Duration		30 ± 5 days	60 ± 14 days	
Visit		801	802-X	

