Relative day within a cycle		Period begins the day after stopping of study treatment and lasts approximately 30 days	Period begins 1 day after short-term follow-up period is completed and continues until death, study withdrawal, or the patient is lost to follow-up	
Procedure Category	Procedure			Comments
Physical Examination	Physical examination (including weight)	X		
	Vital signs	X		Includes blood pressure, pulse, and temperature.
	ECOG performance status	X		
Tumor Assessment	Radiologic imaging according to RECIST 1.1	X		The same method of imaging (CT scan, spiral CT, etc.) used at baseline should be used for each subsequent assessment. Not required if progressive disease is documented while on treatment or if there are clear signs of clinical progression.
	Tumor measurement (palpable or visible)	X		Performed at the same time as radiologic imaging.
Adverse Events Collection/CTCAE Grading		X	X	After Visit 801, only study treatment-related serious events are reported.
Concomitant Medication Notation		X		
Lab/Diagnostic Tests	Hematology	X		
	Chemistry	X		
	ECG	X		
	Exploratory blood sample for biomarkers	X		
	Plasma biomarker sample	X		
	Optional posttreatment biopsy		X	
Health Outcome Measure	Lung Cancer Symptom Scale	X		The LCSS will need to be administered prior to extensive interaction with site personnel.
Follow-Up	Survival Assessment		X	Approximately every 60 (±14) days (telephone assessment is acceptable).

Abbreviations: CT = computed tomography; CTCAE = Common Terminology Criteria for Adverse Events (NCI 2009); ECOG = Eastern Cooperative Oncology Group (Oken et al. 1982); LCSS = Lung Cancer Symptom Scale; RECIST 1.1 = Response Criteria In Solid Tumors Version 1.1 (Eisenhauer et al. 2009).

Table JTJH.2.4. Continued Access Schedule of Activities

	Study Treatment	Follow-Up ^a	
Visit	501-5XX	901	
Procedure ^b			Comments
AE collection	X	X	
Administer LY2606368	X		IV over approximately 60 (+10) minutes once every 14 days.

Abbreviations: AE = adverse event; IV = intravenously.

- a Continued access follow-up begins 1 day after the patient and the investigator agree that the patient will no longer continue treatment in the continued access period and lasts approximately 30 days. No follow-up procedures will be performed for a patient who withdraws informed consent unless he or she has explicitly provided permission and consent.
- b Efficacy assessments will be done at the investigator's discretion based on the standard of care.

3. Introduction

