4.2. Secondary Objectives

- To characterize the safety and toxicity profile of LY2606368
- To characterize the pharmacokinetics (PK) of LY2606368
- To estimate secondary efficacy measures including disease control rate (DCR), duration of response (DoR), progression-free survival (PFS), and overall survival (OS)
- To evaluate the association between best tumor response and change from baseline in lung cancer specific-symptoms, symptomatic distress, activity status, overall quality of life, total Lung Cancer Symptom Scale (LCSS) score, and Average Symptom Burden Index (ASBI) for patients who have platinum-sensitive or platinum resistant/refractory SCLC

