5.3. Handling of Dropouts or Missing Data

The full analysis set, which includes all enrolled patients, will be used for all baseline, efficacy, health outcomes, dosing/exposure, and safety analyses.

Baseline will refer to the last non-missing observation prior to first administration of any treatment unless stated otherwise. Missing data, except for dates, will not be imputed. When dates are used in calculations, missing days will be replaced with 15th of the month and missing day/month with 01 JULY. Where windows are allowed for data collection and there is more than one reading in any window, appropriate consideration will be given as to whether only one value from the window should be used, and if so how it should be chosen. This could either be the mean (geometric mean) or the value closest to the mid-point of the window or the value closest to the data collection time of another variable if the analysis involves time-matched analyses.

If a patient discontinues from study treatment for any reason other than becoming lost to follow-up or death, regular follow-up visits will be conducted to collect information on subsequent non-protocol defined therapy, first disease recurrence, and death. Therefore, it is possible to obtain information for time-to-event endpoints for these patients.

In the primary efficacy analysis, a patient with a tumor response of “not evaluable” will be included in the denominator for the purpose of calculating ORR.

In the health outcomes/quality-of-life analyses, if any of the 6 symptom-specific questions have not been completed, the ASBI will not be calculated. Similarly, if any of the 9 LCSS questions have not been completed, the total LCSS score will not be calculated.

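### The LCSS maximum-improvement model has no visit window, so confirmed responders contribute about twice as many scores as patients who progress at the first scan, and the maximum favours them even if LCSS is unrelated to response

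*SAP*

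**What the plan says.** The objective in SAP 4.2 is "To evaluate the association between best tumor response and change from baseline in lung cancer specific-symptoms", together with symptomatic distress, activity status, quality of life, total LCSS and ASBI. Under SAP 5.11, descriptive statistics "by category of BOR (that is, CR, PR, SD, PD) will be summarized and a linear model will be fitted for each cohort". The section then states: "The model will include change from baseline/maximum change from baseline as the response variable", with BOR category as the independent variable. The preceding sentence describes the second outcome as a maximum improvement. Protocol 10.3.3.8 describes the same model. Neither document names a visit for the plain change, a window for the maximum, or an adjustment for the number of assessments. SAP 5.2 points to 5.11 for covariates, but 5.11 names none besides BOR. SAP 5.3 adds: "Missing data, except for dates, will not be imputed".

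Collection is tied to treatment. Protocol Table JTJH.2.2 schedules the LCSS on Day 1 of every 14-day cycle: "The LCSS is to be administered prior to extensive interaction with site personnel and prior to administration of study drug". Table JTJH.2.3 adds one post-treatment LCSS at Visit 801, in the short-term follow-up period: "Period begins the day after stopping of study treatment and lasts approximately 30 days". No LCSS is scheduled in long-term follow-up. Protocol 8.1 stops treatment at progressive disease.

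**The concern.** BOR is the predictor, but it also helps determine how long the patient stays on treatment and so how many LCSS scores exist. A maximum over more scores is larger on average whenever scores fluctuate between visits. The fitted BOR coefficient therefore mixes any real link between response and symptoms with the unequal number of chances to record a good score. The contrast most affected is confirmed CR/PR against PD, the one most likely to be read as evidence that response brings symptom relief. The planned compliance summary is by cohort, not by BOR group, so it would not show the imbalance.

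**Working it through.** The plan states no power, variance or error rate for this model, so there is no figure to reproduce.

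**Step 1: score counts (no delays).** The pre-dose Cycle 1 Day 1 score is baseline (SAP Table JTJH.5.1). Day 1 of cycle c falls on study day 1 + 14(c − 1): days 15, 29, 43, 57, 71 for cycles 2 to 6. The first scan is at days 8 to 14 of Cycle 3, that is study days 36 to 42, with later scans about every 6 weeks (± 1 week). Confirmation must come more than 4 weeks after the response is first seen (SAP 5.10.1).

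- PD at the first scan: C2D1, C3D1, Visit 801 = 3 scores.
- Response at the first scan, confirmed at the next scheduled scan (days 71 to 84): C2D1 to C6D1 plus Visit 801 = 6. About 9 if progression comes at the third scan.
- Unscheduled confirmation just after 4 weeks (day 36 + 29 = 65), with treatment then stopping: C2D1 to C5D1 plus Visit 801 = 5. If every cycle runs 21 days, the count is also 5 in most cases. PD stays at 3.
- Stable disease: anywhere from about 3 upward. SAP 5.10.2 needs only one qualifying assessment at 5 weeks or later, so a patient who stops soon after the first scan has about 3. Progression at the second scan gives about 6.

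**Step 2: expected maximum under no association.** Assume total standard deviation σ and correlation ρ between any two visits. The within-patient standard deviation is τ = σ√(1 − ρ). The patient's own level cancels in the change score, and the baseline error has mean zero. The expected maximum improvement over k scores is τ·m(k), where m(k) = ∫ x·k·φ(x)·Φ(x)^(k−1) dx. This gives m(3) = 0.846, m(5) = 1.163, m(6) = 1.267, m(9) = 1.485.

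With assumed σ = 15 mm and ρ = 0.5, τ = 15 × √0.5 = 10.6 mm. The spurious CR/PR-minus-PD difference is then:

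- 6 against 3 scores: 10.6 × (1.267 − 0.846) = 4.5 mm
- 9 against 3: 10.6 × (1.485 − 0.846) = 6.8 mm
- 5 against 3: 10.6 × (1.163 − 0.846) = 3.4 mm

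**Step 3: null simulation.** Assumed: 58 patients; CR/PR, stable, PD splits of 9/20/29, 16/20/22 and 6/16/36 (16 and 6 are the final response thresholds in SAP 5.1); a three-group F test at a nominal 5%. Counts are in the order CR/PR, stable, PD.

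| Setting | Counts | CR/PR minus PD | Rejects |
|---|---|---|---|
| ρ = 0.5 | 6/6/3 | 4.4–4.5 mm | 17%–19% |
| ρ = 0.5 | 9/6/3 | about 6.8 mm | 23%–29% |
| ρ = 0.5 | 5/5/3 | about 3.4 mm | about 12% |
| ρ = 0.5, stable-disease counts spread over 3–6 | 6/3–6/3 | about 4.5 mm | 11%–14% |
| ρ = 0.7, worsening 2 mm per visit, between-patient standard deviation of true change 10 mm | 6/6/3 | 1.2–1.5 mm | 5%–6% |
| AR(1) 0.8–0.95 by visit order | 6 or 9/6/3 | 2.7–8.2 mm | about 22%–40% |
| No visit-to-visit variation | unequal | about 0 | about 5% |
| ρ = 0.5, equal counts | 3/3/3 | about 0 | about 5% |

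The last row shows that the unequal counts are the cause. With CR and PR kept as separate categories, as the SAP lists them, the F test rejects in 7% to 24%. Under the null, change at C3D1 rejects in 4.5% to 5.3%, with a difference within 0.15 mm of zero.

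**The case against.** The strongest reply is that the documents never say the maximum runs over all visits. SAP 5.11 ties the tumour-size change to the time point where BOR is observed, so the LCSS window may simply be unspecified. That is true as a matter of wording. But no window is written for the LCSS maximum, and a programmer following the text would take every available score.

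A reader might infer that every patient without PD gains, or that a confirmed response always brings at least 6 scores. The documents support neither. Patients with stable disease gain only as far as they stay on treatment. Protocol 7.2.1 and 7.4 permit cycle delays while Table JTJH.2.2 holds the scan interval, so a confirmed responder can have 5. At 6/6/3, CR/PR and stable disease do not differ.

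The size is also fairly challenged. Standard deviation, correlation, drift and group sizes are all assumed, and ASBI and total LCSS are means of 6 and 9 items that may vary less than single items. Steady worsening, plausible in this disease, shrinks the effect. SAP 5.11 names no test or level, so the 5% test is only a yardstick. These points limit the claimed size; they leave the counts and the direction for confirmed CR/PR against PD intact.

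Finally, plain change from baseline is modelled too. It names no visit, so it does not yet supply a defined alternative.

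**Conclusion.** The concern holds for confirmed CR/PR against PD. Provided scores vary between visits, the maximum-improvement model favours confirmed responders when LCSS is unrelated to response, because about 6 scores (5 in some schedules, more with longer treatment) are set against about 3. The illustrative size is about 1 to 8 mm on a 100-mm scale. Rejection at a nominal 5% is about 17% to 29% with standard deviation 15 mm, correlation 0.5 and stable-disease patients at 6 scores, and 11% to 14% if their counts range over 3 to 6. It is close to nominal when worsening and between-patient variation are added, and the bias vanishes without visit-to-visit variation.

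A reader might go further and conclude that the trial's main result is compromised. It is not: the ORR estimates and decision rules do not use LCSS. This is one stated analysis of a secondary objective. It should be corrected, but nothing in the trial's conduct depends on it.

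**What to change.** In SAP 5.11:

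- (a) Define change from baseline for this model at one named visit common to all BOR groups, for example C3D1, and make that the main analysis.
- (b) Report the all-visit maximum improvement as descriptive only, beside the number of LCSS assessments per BOR group, and use one term for it (improvement is a decrease on this scale).
- (c) Optionally add two sensitivity analyses: a maximum over a common window (C2D1 to C3D1), and a repeated-measures model of all scheduled change scores. In the latter, place Visit 801 at its actual time or leave it out, and state the BOR contrast. Pooling Visit 801 as one visit level introduced an opposite bias of 2.0 to 3.4 mm when scores worsened by 2 mm per cycle.

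The cost is SAP wording and programming, with no new data. Because Protocol 10.3.3.8 carries the same model, Protocol 10.3 requires the change and its justification to appear in the SAP and the clinical study report. There are downsides. C3D1 precedes the first scheduled scan, so it misses later improvement, and patients without that score drop out. The repeated-measures model assumes that scores missing after treatment stops are missing at random, and its late visits come mainly from responders.

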9.9. Health Economics

The primary health outcomes research goal is to evaluate the association between best tumor response and change from baseline in lung cancer-specific symptoms, symptomatic distress, activity status, overall quality of life, total Lung Cancer Symptom Scale (LCSS) score, and Average Symptom Burden Index (ASBI) for patients who have platinum-sensitive or platinum-resistant/refractory SCLC. Patient-reported outcomes and symptoms will be assessed by the LCSS patient scale. The LCSS is a validated tool that has been broadly used in lung cancer research and is available in over 30 different languages.

The LCSS (Hollen et al. 1994) consists of 9 total items, each with a 100-mm line depicting the visual analog scale (VAS). Scores equal the length of line as marked by patient and range from 0 (for best outcome) to 100 (for worst outcome). Six items are symptom-specific measures for lung cancer (appetite loss, fatigue, cough, dyspnea, hemoptysis, and pain) that address 2 dimensions: physical and functional. There are also 3 summation items that describe symptomatic distress, activity status, and overall quality of life.

The LCSS will be administered as shown in the Schedule of Activities (Section 2). The LCSS will be completed by patients when a language translation is available in which the patient is fluent or literate. The recall period is 24 hours and the typical completion time is 8 minutes initially for demonstration of VAS; 3 to 5 minutes for subsequent administrations. To avoid biased responses, the questionnaires should be administered prior to extensive contact with study personnel and clinicians and prior to study drug administration.

10. Statistical Considerations

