5.1. General Considerations

Statistical analysis of this study will be the responsibility of Eli Lilly and Company. The interpretation of the study results will be the responsibility of the Lilly Clinical Research Physician/Clinical Research Scientist (CRP/CRS) and statistician. The CRP/CRS and statistician will also be responsible for the appropriate conduct of internal reviews for both the final study report and any study-related material to be authorized by Lilly for publication.

Any change to the data analysis methods described in the protocol will require an amendment ONLY if it changes a principal feature of the protocol. Any other change to the data analysis methods described in the protocol and the justification for making the change will be described in the clinical study report.

The study will enroll approximately 116 patients (58 platinum-sensitive patients, 58 platinum-refractory/resistant patients).

For the platinum-sensitive cohort, it is assumed that a true ORR of less than 20% indicates inadequate antitumor activity. Given that a futility interim analysis will be conducted on the first 29 patients' response data, then with a one-sided significance level of 0.1, a sample size of 58 patients will provide approximately 90% power to detect a true ORR of at least 35%.

For the platinum-refractory/resistant cohort, it is assumed that a true ORR of less than 5% indicates inadequate anti-tumor activity. Given that a futility interim analysis will be conducted on the first 29 patients' response data, then with a one-sided significance level of 0.1, a sample size of 58 patients will provide approximately 90% power to detect a true ORR of at least 15%.

The stopping rule for interim analysis and decision rule for final analysis are defined as follows:

- Platinum-sensitive cohort:
 - If 4 or fewer overall responses of confirmed CR or PR are observed in the first 29 patients, then the cohort will be terminated for futility; otherwise, the cohort will continue
 - If 16 or more overall responses of confirmed CR or PR are observed in all 58 patients, then the ORR is statistically significantly greater than 20%
- Platinum-refractory/resistant cohort:
 - If no overall response of confirmed CR or PR is observed in the first 29 patients, then the cohort will be terminated; otherwise, the cohort will continue
 - If 6 or more overall responses of confirmed CR or PR are observed in all 58 patients, then the ORR is statistically significantly greater than 5%

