Analyses will be implemented using Statistical Analysis System (SAS[®], SAS Institute) version 9.1 or higher; any exceptions will be documented in the outputs.

The following data handling conventions will be used in the analysis (see [Table JTJH.5.1](#)).

Table JTJH.5.1. Data Handling Conventions

Term	Definition or Rule
Relative Study Day	If assessment is on or after date of first dose then (date of assessment) – (date of first study treatment dose) +1
	If assessment precedes first dose of drug then (date of assessment) – (date of first study treatment dose)
	There is no Study Day 0. Study Day 1 is the date of first dose and study day -1 is the day before the first dose.
Baseline	For change from baseline analyses, baseline value is defined as the last reported measure on or before the first dose date (prior to the dose administration), unless otherwise specified. For change from baseline within a cycle, baseline value is defined as the measure prior to the first dose of that cycle, unless otherwise specified.
Entered	Patients who have signed the informed consent form directly or through their legally acceptable representatives.
Enrolled	Patients who have been assigned to study treatment and have received at least one dose of study treatment.
Screen Failures	Patients who have signed informed consent, do not meet eligibility criteria and are not enrolled.

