5.2. Adjustments for Covariates

Please refer to Sections [5.11](#) and [5.17.1](#) for analyses with adjustments for covariates.

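### The LCSS change models use best overall response as their only explanatory term; the baseline-adjusted model should be fitted and reported beside the unadjusted one, and two loose definitions tightened

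*SAP*

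**What the plan says.** The secondary objective in SAP 4.2 is: "To evaluate the association between best tumor response and change from baseline in lung cancer specific-symptoms", together with the summation items, total LCSS and the Average Symptom Burden Index (ASBI). Protocol 9.9 says that item scores "range from 0 (for best outcome) to 100 (for worst outcome"), so lower is better and improvement stops at 0.

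SAP 5.11 gives the method: "a linear model will be fitted for each cohort in order to evaluate the association between BOR and change from baseline/the maximum improvement". The sentence that follows sets out the model: "The model will include change from baseline/maximum change from baseline as the response variable and category of best overall response as an independent variable". Protocol 10.3.3.8 gives the same model. Neither section names a baseline score or any other adjusting variable.

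SAP 5.2 nevertheless refers the reader to 5.11 and 5.17.1 "for analyses with adjustments for covariates". The covariate is available. LCSS is scheduled at screening and before dosing on Day 1 of Cycle 1 (protocol Tables JTJH.2.1 and 2.2), and SAP Table JTJH.5.1 says: "baseline value is defined as the last reported measure on or before the first dose date (prior to the dose administration").

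SAP 5.11 also defines change in tumour size (CTS) as the percent change from baseline to the evaluation at which best response is seen, and adds: "The correlation between CTS and LCSS score and ASBI will be tested using the Spearman's correlation coefficient".

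**The concern.** Best overall response (BOR) categories are formed after baseline and not by randomisation, so nothing makes their starting symptom scores alike. A patient who starts with a high score has more room to improve and, on average, some tendency to drift back towards the mean. If responders and non-responders start at different levels, a comparison of change by BOR can mix that starting difference with any real link between tumour response and symptoms. The direction is unknown, so an association could be created or hidden.

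Two wordings in the same section add uncertainty. The model sentence speaks of maximum change where the sentence before it speaks of maximum improvement. The Spearman sentence names the score, while the objective is change from baseline, and it gives no visit. If a programmer used the raw score, baseline severity would enter the correlation directly.

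**Working it through.** **Plan's own figure.** There is none to reproduce. The documents give no SD, correlation, effect size or power for the LCSS models.

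**Inputs from the documents.** SAP 5.1: "The study will enroll approximately 116 patients (58 platinum-sensitive patients, 58 platinum-refractory/resistant patients"). Design response rates are 35% and 15%, so there would be about 0.35 × 58 ≈ 20 responders against 38 others, and 0.15 × 58 ≈ 9 against 49. Splitting into CR, PR, SD and PD makes the groups smaller still.

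**Assumed inputs, not in the documents.** Score SD 20 mm; equal variance at baseline and follow-up; baseline-to-follow-up correlation r of 0.3 to 0.7; baseline difference d between responders and others of 5 or 10 mm.

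**Step 1: how large could a baseline difference be by chance?** The standard error of the difference is SD × √(1/n₁ + 1/n₂).
- 20 v 38: 20 × √(1/20 + 1/38) ≈ 5.5 mm.
- 9 v 49: 20 × √(1/9 + 1/49) ≈ 7.3 mm.

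A 10 mm difference would therefore not be surprising even with no systematic cause.

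**Step 2: what each model estimates.** Let d be the baseline difference between groups and e the follow-up difference. With equal variances the within-group slope is r.
- Unadjusted contrast of change: e − d.
- Baseline-adjusted contrast: e − r·d.
- Gap between them: (1 − r)·d, whatever the truth.

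There are two ways for response to have no real link with symptom change:
- *All groups regress to a common mean*, so e = r·d. The unadjusted contrast is −(1 − r)·d and the adjusted contrast is 0.
- *Each group keeps its own stable mean*, so e = d. The unadjusted contrast is 0 and the adjusted contrast is (1 − r)·d.

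| r | (1 − r) × 10 mm | (1 − r) × 5 mm | Residual variance, adjusted ÷ unadjusted = (1 − r²)/[2(1 − r)] = (1 + r)/2 |
|---|---|---|---|
| 0.3 | 7 | 3.5 | 0.65 |
| 0.5 | 5 | 2.5 | 0.75 |
| 0.7 | 3 | 1.5 | 0.85 |

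**Step 3: simulation under each assumption** (20 v 38 patients, SD 20, 4,000 runs per setting, two-sided 5% tests for illustration, since the plan sets no level for this association).
- *Common mean*, baseline mean 35, scores clipped to 0–100, responders starting 10 mm worse, slope 0.7 to 0.5. The unadjusted model showed 3.1 to 5.0 mm of false improvement for a single follow-up, with rejection in 11% to 14% of runs. For maximum improvement over four visits it showed 3.4 to 5.3 mm and 18% to 24%. With baseline added, bias stayed within about 0.2 mm and rejection between 4% and 5.5%. With no baseline difference, neither model was biased.
- *Stable group means* 10 mm apart, r = 0.3, 0.5, 0.7. The unadjusted model had bias of about 0 and rejected in 4% to 5% of runs. The adjusted model was off by 7.0, 5.1 and 3.0 mm and rejected in 24%, 16% and 11%.

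**Step 4: the Spearman sentence against the objective.** One variable is a percent change from baseline. The other is named only as the score, with no visit. SAP 4.2 asks about change from baseline on the symptom side as well.

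**The case against.** The strongest reply is that the planned model answers the stated objective. SAP 4.2 asks how response relates to change from baseline, and mean change by BOR estimates that directly. Adjusting for baseline targets a different, conditional quantity. With non-randomised groups neither is unbiased by design (Lord's paradox), and Step 3 shows the adjusted model going wrong when groups have stable differences. This stands. It rules out replacing one model with the other, but it does not rule out showing both.

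A reader might infer from SAP 5.2 that a covariate was intended and then left out. The evidence for that is weak: 5.17.1, the other section it names, lists no adjusting covariate either, so 5.2 may use the word loosely for any regressor. What stands is that 5.11 as written contains no adjustment, because BOR is the factor under study. The model sentence does not say it is exhaustive, but no further term is named anywhere.

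A reader might take maximum change, on a lower-is-better scale, to mean the worst deterioration. The preceding sentence points to maximum improvement, so this needs a clarification and is not an error of method. Likewise, the Spearman sentence does not prove that raw scores will be used; it leaves that open.

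**Conclusion.** The point holds in a limited form. The LCSS models omit an available baseline score, and the result could depend on that choice by (1 − r)·d: about 3 to 7 mm for a 10 mm baseline difference, or 1.5 to 3.5 mm for 5 mm, under assumed equal variances and r between 0.3 and 0.7. If baseline scores do not differ by BOR, there is no bias either way.

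It would be tempting to conclude that the planned analysis is biased by 3 to 7 mm and that adjustment cures it. The documents do not support this. They give no LCSS data by response category, and the size and location of the bias depend on whether groups regress to a common mean, which is not known.

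Nor should the floor at 0 be read as solved by adjustment. A linear baseline term does not model a floor. It also does not remove the advantage that patients with more visits have on maximum improvement.

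This is a secondary objective with no stated power or decision rule, and the ORR rules in SAP 5.1 are untouched.

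**What to change.** In SAP 5.11, with protocol 10.3.3.8 kept consistent:

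1. Add to each linear model the baseline value of the same item, ASBI or total LCSS, and report it alongside the unadjusted change by BOR. Say beforehand that a gap between the two will be read as dependence on baseline differences. This also brings 5.11 into line with 5.2. If the sponsor keeps only the unadjusted model, the pointer in 5.2 should be corrected instead.
2. State that the model's maximum change is the maximum improvement: baseline minus the lowest post-baseline score.
3. Run the Spearman correlation of tumour-size change against change from baseline in total LCSS and in ASBI, at the visit nearest the scan used for the tumour-size change.

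The cost is a few lines of text, one degree of freedom per model, and two estimates that may differ and must then be explained. No new data are needed.
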